## 8.0 PRETREATMENT EVALUATION

### 8.1 Documentation of tests resulted and/or verification to be performed within 28 days of starting treatment.

- Record prior medications and treatments
- Record prior anti-cancer therapy
- Physical examination
- ECOG performance status
- 12 lead electrocardiogram (ECG)
- Complete metabolic panel, including magnesium and phosphorus
- Lactate dehydrogenase (LDH)
- Serum/urine protein electrophoresis (SPEP/UPEP), serum/urine immunofixation, and serum free light chain (**multiple myeloma patients only**)
- Bone marrow biopsy and aspiration (**multiple myeloma patients only**)
- PET/CT or CT Chest, Abdomen, and Pelvis (B-cell lymphoma, PTCL, CTCL with extracutaneous disease)
- Register patient with REMS® program.

- mSWAT for patient with cutaneous lymphoma.
- Sezary panel in patients with Sezary syndrome only.
  - Peripheral blood flow cytometry with immunoconjugates for CD2, CD3, CD4, CD8, CD26 and or CD7, and CD52.
- Pregnancy testing for females of childbearing potential within 10-14 days and again 24 hours prior to prescribing lenalidomide per the [Revlimid REMS® program](#).

## **8.2 Documentation of tests resulted and/or verification to be performed within 14 days of starting treatment.**

- Complete blood count (CBC)

## **9.0 TREATMENT/INTERVENTION PLAN**

### **9.1 Pretreatment electrolyte assessment and drug management**

Prior to initiation of each dose of romidepsin the patients level of potassium (K+) and magnesium (Mg) must be confirmed to be within normal range or if low, supplement as per outlined in sections 10.1 and 10.2. In cycle 2 and beyond, magnesium and potassium levels may be checked up to 2 days before romidepsin. If within treatment range, they do not need to be repeated prior to romidepsin administration unless clinically indicated. Intravenous (IV) supplementation with potassium chloride (KCL) and/or magnesium sulfate can be used. If supplementation is necessary, documentation of levels after IV supplementation is required. Supplementation with oral KCL or magnesium oxide (MgOX) or magnesium soy (MgSoy) can be used. These parameters apply to both the phase Ib and IIa portion of the study.

### **9.2 Treatment plan romidepsin/lenalidomide Phase Ib**

Subjects enrolled into the phase 1b portion will enroll at dosing level 1 with three patients per dosing level (3X3 design) as described in Table 2 below.

Dose Level	Romidepsin	Lenalidomide
-1	8 mg/m 	10 mg
1	8 mg/m 	15 mg
2	8 mg/m 	25 mg
3	10 mg/m 	25 mg
4	14 mg/m 	25 mg

**Table 2: Description of dose level.**

If all three patients complete one cycle of therapy without a DLT at the respective dose level then the subsequent dose level can be accrued. A DLT is defined in section 4.1. After the MTD is determined by either DLT or accrual of six patients without DLT at dose level 4 in the first cycle accrual to the phase Ib portion will be considered closed. The MTD from the phase Ib study will be used for the initial starting doses for both romidepsin and lenalidomide. The treatment plan is described below for the phase Ib portion:

Romidepsin/Lenalidomide Cycle 1 Day 1

Romidepsin IVPB over 4 hours

Lenalidomide PO q days 1-21

Romidepsin/Lenalidomide Cycle 1 Day 8

Romidepsin IVPB over 4 hours

Romidepsin/Lenalidomide Cycle 1 Day 15

Romidepsin IVPB over 4 hours

**\*1 cycle equals 28 days**

### **9.3 Treatment Plan romidepsin/lenalidomide Phase IIa**

The entire accrual is planned to have up to 51 patients in the phase IIa portion; each disease cohort will have 15 patients (B-cell lymphoma, multiple myeloma or PTCL). There will be an expansion of the T-cell cohort to include an additional 6 patients with acute T-cell leukemia/lymphoma. After a sufficient number of patients have been enrolled for determination of the primary and secondary objectives, cohorts may be closed to accrual by the MSK principal investigator. The MTD for lymphoma has been determined to be 14mg/m^2 romidepsin on Days 1, 8, 15 and 25mg lenalidomide from Days 1-21. The patients treated at MTD in the phase Ib cohort (if measurable disease at enrollment) and phase IIa cohort will be evaluated both collectively and by disease subtype. Patients with more than one histology are eligible and will be assigned by the principal investigator to a specific disease subtype.

- In patients with MM, due to the presence of toxicities, patients will be dosed at romidepsin 10mg/m^2 and lenalidomide 25mg (see table 2a). If two of six (or fewer) patients treated at this dose level develop dose-limiting toxicities, the initial dosing for subsequent patients will be decreased to romidepsin

10mg/m^2 and lenalidomide 15mg. For example, if two of four patients treated at this initial dose develop dose-limiting toxicities, the starting dose for subsequent patients will be reduced as above.

- At a starting dose of romidepsin 10mg/m^2 and lenalidomide 15mg, should 2 of 6 (or less) patient will be reduced to romidepsin 8mg/m^2 and lenalidomide 15mg.
- At a starting dose of romidepsin 8mg/m^2 and lenalidomide 15mg, should 2 of 6 (or less) patients have dose-limiting toxicities, the initial dose for subsequent patients will be reduced to romidepsin 8mg/m^2 and lenalidomide 10mg.

Table 2a: Multiple Myeloma Dosing for Phase IIa Portion

Dose level	Romidepsin	Lenalidomide
1	10	25
-1	10	15
-2	8	15
-3	8	10

The treatment plan for the phase IIa portion is described below:

Romidepsin/Lenalidomide Cycle 1 Day 1 + subsequent Cycle X

Romidepsin MTD IVPB over 4 hours

Lenalidomide MTD PO q days 1-21

Romidepsin/Lenalidomide Cycle 1 Day 8

Romidepsin MTD IVPB over 4 hours

Romidepsin/Lenalidomide Cycle 1 Day 15

Romidepsin MTD IVPB over 4 hours

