- Grade 4 hematologic toxicities (attributed to study drugs) defined as:
  - Grade 4 thrombocytopenia (platelets  $< 25$  K/ $\mu$ L)
  - Grade 4 neutropenia (absolute neutrophil count (ANC)  $< 0.5$ )
- Grade 3 thrombocytopenia or neutropenia that results in a  $> 4$  day delay in any romidepsin dose in cycle 1.
- One week or greater delay in initiating cycle 2 day 1 due to continued drug-related toxicity.

At the time of enrollment the patients will be identified as representing three cohorts based upon disease subtype: 1) B-cell lymphoma 2) multiple myeloma 3) PTCL. Each disease specific cohort will enroll 15 patients. We plan to accrue 38 patients into the phase IIa portion including those treated at the MTD of the phase Ib portion. The assessment of toxicity and efficacy will be performed within the entire cohort evaluable at MTD. A preplanned exploratory analysis of the toxicity and efficacy of the disease specific cohorts will also be performed. Efficacy measures which will be determined include ORR, CBr (for myeloma), TTR, DOR, and EFS. ORR is defined as the percentage of patients achieving a best response of CR/CRu, very good partial response (VGPR--myeloma only), or PR at any disease assessment time point. CBr is defined as CR, VGPR, PR or MR (minimal response) in myeloma patients. TTR is defined as the time or number of cycles between study registration and documentation of first response (CR/Cru, VGPR, or PR). DOR is defined as the time or number of cycles between documentation of first response and progression, change of therapy, death, or date of last contact (if still alive without progression). EFS is defined as the time between study registration and documented progression, change in therapy, or death if no progression was observed.

[figure not shown]

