## 14.0 BIOSTATISTICS

The standard dose-escalation scheme for this study is as follows. Patients will be accrued to the study in cohorts of 3. For any given dose an initial cohort of 3 patients will be treated at that dose. The dose level will be escalated if none of the 3 patients exhibits any DLT in the first cycle as defined in section 4.1. If a DLT is observed in one patient, an additional cohort of 3 patients will be treated at that dose. The dose will be escalated if none of the additional 3 patients exhibits any DLT. Dose-escalation stops and the previous dose will be considered the MTD if 2 or more patients have a DLT. If the previous dose level has been administered to only 3 patients, an additional 3 patients will be enrolled to confirm the result. For this design the probability of escalation is as follows:

True toxicity rate	5%	10%	15%	20%	25%	30%	40%	50%
Probability of escalation	0.97	0.91	0.81	0.71	0.60	0.49	0.31	0.17

Dose escalation will start with dose level 1. A dose level -1 is also added to the design to ensure a minimum level of toxicity (we expect this dose level will be quite tolerable for patients). The maximum number of patients needed for this dose escalation design is 30. Patients with measurable disease treated at MTD in the phase Ib will be analyzed in phase Ila to further characterize the toxicity of romidepsin and lenalidomide in combination at the MTD determined by phase Ib. In phase Ila, we plan to enroll about 39 patients so that the total number of patients to be treated at MTD will be approximately 44 (we plan to enroll 15 patients with B-cell lymphomas, 8 patients with multiple myeloma, 15 patients with T-cell lymphomas and additional 6 patients with acute T-cell leukemia/lymphoma). To subsequently monitor the safety primary endpoint in the phase Ila portion, we will employ a dose-reduction plan for the predefined DLT in the phase Ib portion during cycles 1-4. This dose-reduction plan specifies that the dose will be reduced from the phase Ib MTD to the MTD-1 (10mg/m^2 romidepsin; 25mg lenalidomide) if DLT occur in cycle 1-4 in: ≥8/first 15; ≥16/first 30; or if more than 24 patients when the last (45th) evaluable patient has completed the trial have any DLT. If at MTD-1 a DLT occurs in ≥8/first 15; ≥16/first 30, then MTD-2 (8mg/m^2 romidepsin; 25mg lenalidomide) will be employed for the remainder of phase Ila. The probability of dose-reducing from the MTD is the following:

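### The myeloma cohort is 15 in Sections 4.1 and 9.3 but 8 in Section 14, so the phase IIa totals and the last safety look disagree; Section 14 also does not say whether it covers myeloma

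*Combined protocol and SAP*

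**What the plan says.** Doses are written as romidepsin mg/m² / lenalidomide mg.

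**Cohort size and totals**

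- Section 4.1: "Each disease specific cohort will enroll 15 patients", for B-cell lymphoma, multiple myeloma and PTCL. The next sentence reads "We plan to accrue 38 patients into the phase" IIa portion, including phase Ib patients treated at the MTD.
- Section 9.3: "The entire accrual is planned to have up to 51 patients in the phase" IIa portion. It repeats 15 per cohort, names myeloma, and adds 6 patients with acute T-cell leukemia/lymphoma. The principal investigator may close cohorts early.
- Section 14: about 39 patients are enrolled so that the "total number of patients to be treated at MTD will be approximately 44". The split is 15 with B-cell lymphoma, "8 patients with multiple myeloma, 15 patients with T-cell lymphomas and additional 6 patients with acute T-cell leukemia/lymphoma".
- Section 14, looks: the dose is reduced at 8 or more DLTs in the first 15, at 16 or more in the first 30, or if more than 24 patients, when the last (45th) "evaluable patient has completed the trial have any DLT".

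**Dose steps**

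- Section 9.3 calls 14/25 the MTD for lymphoma and starts phase IIa myeloma patients at 10/25 because of toxicity. The myeloma rule is "If two of six (or fewer) patients treated at this dose level develop dose-limiting toxicities, the initial dosing for subsequent patients will be decreased", and Table 2a runs 10/25, 10/15, 8/15, 8/10.
- Section 9.7 refers the reader to Section 14 for the phase IIa toxicity rule.
- Section 14 steps from 14/25 to 10/25. If the limits are met again, 8 mg/m² romidepsin with "25mg lenalidomide) will be employed for the remainder of phase" IIa.

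**The concern.** Two planned sizes for one cohort cannot both hold. The size fixes the accrual total and the precision of the myeloma response and clinical benefit rates. It also affects the safety monitoring, because the last look is tied to a patient number that fits none of the stated totals.

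The second matter is scope. Safety is the primary objective, and myeloma patients start below the lymphoma MTD. Section 14 lists them among patients treated at the MTD, does not mention Table 2a, and does not say whether their DLTs enter the looks at 15, 30 and 45 patients. Whoever applies those looks must decide this without guidance, and the decision affects when lymphoma patients are reduced.

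**Working it through.** **1. Totals.** Inputs are the cohort sizes quoted from Sections 4.1, 9.3 and 14.

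| Myeloma n | Three cohorts | Plus 6 acute T-cell leukemia/lymphoma | Agrees with |
|---|---|---|---|
| 8 | 15 + 8 + 15 = 38 | 44 | 4.1's total of 38; Section 14's 44 |
| 15 | 3 × 15 = 45 | 51 | 9.3's 51 |

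Section 14's 44 is reproduced with 8 myeloma patients and 9.3's 51 with 15. Section 4.1 disagrees with itself: its cohort size gives 45 and its total is 38. It does not give the split behind 38, so the 8 there is inferred. The gap throughout is 15 − 8 = 7. The 45th-patient look equals 3 × 15 but matches neither 44 nor 51.

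The overall total of 67 in Section 1 leaves 67 − 44 = 23 or 67 − 51 = 16 patients outside the phase IIa count. The plan does not show which is meant.

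**2. Precision.** The exact (Clopper-Pearson) 95% upper limit with 0 responders in n is 1 − 0.025^(1/n).

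- n = 8: 1 − 0.025^(1/8) = 36.9%
- n = 15: 1 − 0.025^(1/15) = 21.8%

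Near one half, the interval is 15.7% to 84.3% for 4/8 and 26.6% to 78.7% for 8/15.

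**3. Section 14's reduction table.** An exact binomial recursion with limits 8/15, 16/30 and 25/45 gives 0.052, 0.241 and 0.607 at true DLT rates of 30%, 40% and 50%. The plan prints 0.056, 0.243 and 0.632. Agreement is close except at 50%, where a limit of 24 or more in 45 would give 0.630. Nothing below depends on that difference.

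**4. How often Section 14 would reach 8/25.** Assume the same DLT rate at each dose, outcomes known at once, and looks at exactly 15 and 30 patients. With 44 patients, the only route is 8 or more of 15 at 14/25 (29 patients left), then 8 or more of 15 at 10/25 (14 left). After a crossing at 30, the 14 remaining are too few for another look.

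| True DLT rate | P(≥8/15) | Squared: P(reach 8/25), N = 44 | N = 51 |
|---|---|---|---|
| 30% | 0.0500 | 0.0025 | 0.0027 |
| 40% | 0.2131 | 0.0454 | 0.0564 |
| 50% | 0.5000 | 0.2500 | 0.3389 |

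The N = 51 column adds the routes through a first crossing at 30 patients, which has probability 0.0019, 0.0258 and 0.0889. At 40%: 0.2131 × (0.2131 + 0.0258) + 0.0258 × 0.2131 = 0.0564.

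**5. Cost of limiting the looks to lymphoma.** Planned lymphoma patients number 15 + 15 + 6 = 36, so only the looks at 15 and 30 remain. The chance of reducing from the MTD becomes 0.2131 + 0.0258 = 0.239 at 40% (from 0.241) and 0.5000 + 0.0889 = 0.589 at 50% (from 0.607).

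**The case against.** **On cohort size.** Section 9.3 says up to 51 and allows early closure, so a final myeloma count below 15 would be consistent with it. Section 14 calls 44 approximate, so a look at 45 is only one patient out. These points soften the conflict but do not remove it. A clause allowing a cohort to stop early does not turn a stated 15 into a planned 8, and it does not explain 45 against 38 within Section 4.1.

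**On dosing.** A reader might infer that the protocol prescribes two rival next doses for myeloma, or that Section 14 could raise lenalidomide to 25 mg in a cohort already lowered to 15 or 10 mg. The documents do not support this. Section 9.3 ties 14/25 to lymphoma and gives myeloma its own start and its own titled table. Section 14 describes a dose-reduction plan from the phase Ib MTD, and using it to raise a dose would defeat its purpose. The specific rule most plausibly governs. That leaves the missing statement of scope and the silence on counting.

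The probabilities of reaching 8/25 are also generous. The DLT window is cycles 1-4, 16 weeks or about 3.7 months. At Section 16.0's rate of about 2 patients a month, some 7 more enrol while a look matures (3.7 × 2 = 7.4). Then 15 + 7 + 15 + 7 = 44, and no one is left to start at 8/25 unless accrual is paused or the limit is reached early.

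**On gaps in the myeloma rule.** A reader might infer that myeloma patients are unprotected after the sixth patient at a dose, or at the lowest level. Stopping at six can reasonably mean that the dose is kept, and individual modification and removal under Section 9.7.1 still apply.

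**Conclusion.** The cohort-size conflict is definite. Myeloma is 15 or 8, the phase IIa totals are 38, about 44 and up to 51, and the last look is at a patient number that fits none of them. The size moves the upper limit for zero responders from 21.8% (n = 15) to 36.9% (n = 8), so it matters to the secondary efficacy estimates.

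The dosing point is secondary and less certain. Table 2a is probably the myeloma rule, but Section 9.7 points elsewhere, and Section 14 lists myeloma patients as treated at the MTD without exempting them or saying whether their DLTs count. Section 14's 8/25 step has probability of at most about 0.3%, 4.5% and 25% at true DLT rates of 30%, 40% and 50%. This assumes 44 patients, immediate outcomes, looks at exactly 15 and 30, and an unchanged rate after reduction. It matters only when toxicity is high. The documents should be corrected on both points, the first with high confidence.

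**What to change.** **State one myeloma cohort size and carry it through.**

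- If 8: in Section 4.1, change the 15 for myeloma and add the 6 acute T-cell leukemia/lymphoma patients (38 becomes 44). In Section 9.3, change 15 to 8 for myeloma and 51 to 44. In Section 14, correct the 45th-patient look.
- If 15: in Section 4.1, change 38 (51 with the 6 added). In Section 14, change 8 to 15, 44 to 51, and 39 to 46 if the same 44 − 39 = 5 phase Ib patients carry over. Correct the last (45th) look here too.
- In either case, check the 67 in Section 1 and show how it is built.

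**State the scope.** Add to Sections 9.7 and 14 that Table 2a alone sets the myeloma starting dose, and that Section 14's steps and looks apply to lymphoma patients, who start at 14/25. With 36 planned lymphoma patients the 45-patient look then goes. If the sponsor prefers to pool myeloma into the looks, say so and set the last look at the agreed total.

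**Tidy-up.** The level -1 bullet in Section 9.3 lacks its DLT condition in the text as read. Restore it from the level -2 bullet if it is missing in the source.

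**Cost.** An amendment to wording. Limiting the looks to lymphoma lowers the chance of reducing from the MTD from 0.241 to 0.239 at a true 40% DLT rate, and from 0.607 to 0.589 at 50%.

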**\*1 cycle equals 28 days**

## **9.4 Lenalidomide administration**

In either phase of the study patients will be asked to take the lenalidomide at approximately the same time each day. Prescriptions for lenalidomide must be signed and filled within 7-14 days prior to next cycle of therapy. If a dose of lenalidomide is missed, it should be taken as soon as possible on the same day. If it is missed for the entire day, it should not be made up. A medication diary will be provided to the patient and asked to be returned prior to each cycle . Any pills not used must be returned and all pills must be accounted for.

Patients who take more than the prescribed dose of lenalidomide should be instructed to seek emergency medical care if needed and contact study staff immediately.

## **9.5 Prophylactic Measures**

- Subjects should receive prophylactic anti-emetics prior to romidepsin administration (ondansetron preferred).
- Phase Ib: After cycle 1, G-CSF (filgrastim) may be given at the discretion of the treating physician (phase Ib).
- Phase IIa: G-CSF (filgrastim) may be given at the discretion of the treating physician.

## **9.6 Concomitant Medications**

Patients will be instructed not to take any additional medications (including over-the-counter products) during the trial without prior consultation with their treating physician. All medications taken within 30 days of screening and medications and supportive therapies that are administered during the study must be recorded in the patient's clinical research database (CRDB) and in the source documents. Supportive therapy, that is ongoing at baseline, will be permitted during the treatment phase of the study. If other therapy for the disease is required, continuation of the study treatment should be discussed with the lead investigator. Concomitant medications for other medical conditions are permitted as clinically indicated subject to specific protocol requirements outlined below.

### **9.6.1 Prohibited/monitored concurrent therapy**

- Any investigational agent other than lenalidomide or romidepsin.
- Any medications at high risk of causing QTc prolongation or inducing torsades de pointes (as listed in Appendix F).
- Concomitant use of CYP3A4 inhibitors with romidepsin should be avoided (excluding anti-emetics) to prevent potential increase in romidepsin exposure during concomitant treatment with these drugs. Should a patient already enrolled on this study require treatment with a drug listed in

Appendix G romidepsin must be interrupted prior to starting these drugs and should not resume until a washout period of at least 5 half-lives has elapsed.

Any medications that have the potential to alter serum electrolytes (e.g., diuretics) should be monitored very closely for electrolyte abnormalities as these can contribute to the risk of QTc prolongation and ventricular arrhythmias.

## **9.7 Dose Continuation, Modification and Interruption**

Subjects will be evaluated for AEs at each visit with the NCI CTCAE v4.0 (Appendix H): NCI CTCAE v4.0) used as a guide for the grading of severity. DLTs as defined will be tabulated in cycle 1 of the phase Ia and cycles 1-4 of the phase IIa portion of the study. The toxicity decision rule for the IIa portion is described in Section 14.0. The sections below describe dose reduction steps, instructions for initiation of a new cycle of therapy and dose modifications during a cycle of therapy. Inability to meet treatment criteria will result in holding the dose.

### **9.7.1 Instructions for Dose Modifications or Interruption During a Cycle**

Dose delay and dose reduction rules for lenalidomide and romidepsin are as follows and summarized in the tables 3, 4, & 5:

- In the event of dose reduction due to hematologic toxicity attributed to study drugs, lenalidomide and romidepsin will be reduced as per Tables 3 & 4.
- In the event of dose reduction due to non-hematologic toxicity attributed to study drugs, lenalidomide and romidepsin will be reduced one level per Tables 3 & 4.
- Missed doses of lenalidomide and/or romidepsin are not made up.
- Interruptions of therapy, including delays in starting a new cycle, of greater than 28 days will result in removal from study.
- Patients remaining on treatment after cycle 6, at the discretion of their physician, may elect to receive romidepsin on a day 1 and 15 schedule each cycle.
  - Patients remaining on treatment after cycle 9, at the discretion of their physician may elect to receive romidepsin on day 1 of each cycle (q4 week dosing) after discussion with the MSK Principal Investigator.
- If a patient is at the lowest dose level and deriving benefit from therapy, they may continue on protocol therapy despite  $\geq$  grade 3 hematologic toxicity or non-clinically significant non-hematologic toxicity after discussion with the MSK principal investigator.

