**TABLE 5: Dose Modifications for Lenalidomide and Romidepsin**

NCI CTC Toxicity Grade	Dose Modification Instructions (also see Instructions for Initiation of a New Cycle above)
Grade 3 neutropenia not associated with fever	
 
• Hold lenalidomide and romidepsin dose.
 
• Follow CBC at least weekly.
 
• Upon recovery to grade <math>\leq</math> 2 resume romidepsin and lenalidomide at one dose reduction.
 
• Omitted doses are not made up (Romidepsin doses may be given up to 3 days late).
 

Grade 3 neutropenia associated with fever (temperature <math>\geq 38.5^{\circ}</math> C) or Grade 4 neutropenia	
 
• Hold lenalidomide and romidepsin dose.
 
• Follow CBC at least weekly.
 
• Upon recovery to <math>\leq</math> grade 2 resume lenalidomide and romidepsin at next lower dose level.
 
• Omitted doses are not made up. (Romidepsin doses may be given up to 3 days late)
 

Thrombocytopenia <math>\geq</math>Grade 3 (platelet count <math>< 50,000/\text{mm}^3</math>)	
 
• Hold lenalidomide and romidepsin dose.
 
• Follow CBC at least weekly.
 
• Upon recovery to <math>\leq</math> grade 2 resume lenalidomide and romidepsin at next lower dose level.
 
• Omitted doses are not made up. (Romidepsin doses may be given up to 3 days late)
 

Non-blistering rash	
Grade 3	
 
• If Grade 3, hold lenalidomide dose. Follow at least weekly.
 
• If the toxicity resolves to grade 1, resume lenalidomide at next lower dose level.
 
• Omitted doses are not made up.
 

Grade 4	
 
• If Grade 4, discontinue lenalidomide. Remove patient from study.
 

Desquamating (blistering) rash- any Grade	
 
• Discontinue lenalidomide. Remove patient from study.
 

Neuropathy	
Grade 3	
 
• If Grade 3, hold lenalidomide dose. Follow at least weekly.
 
• If the toxicity resolves to grade 1 resume lenalidomide at next lower dose level.
 
• Omitted doses are not made up.
 

Grade 4	
 
• If Grade 4, discontinue lenalidomide. Remove patient from study.
 

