Venous thrombosis/embolism <math>\geq</math> Grade 3	
 
• Hold lenalidomide and romidepsin. Start therapeutic anticoagulation, if appropriate.
 
• Restart lenalidomide and romidepsin at investigator's discretion after discussion with PI (reduce 1 dose level of each drug).
 
• See Anticoagulation Consideration
 

TABLE 5: Dose Modifications for Lenalidomide and Romidepsin	
NCI CTC Toxicity Grade	Dose Modification Instructions (also see Instructions for Initiation of a New Cycle above)
Hyperthyroidism or hypothyroidism	

• Omit lenalidomide for remainder of cycle, evaluate etiology, and initiate appropriate therapy.

• See Instructions for Initiation of a new cycle and reduce the dose of lenalidomide by 1 dose level.

Other non-hematologic toxicity <math>\geq</math> Grade 3	

• Hold lenalidomide and romidepsin dose. Follow at least weekly.

• If the toxicity resolves to <math>\leq</math> grade 2 resume lenalidomide and romidepsin at one dose reduction.

• Omitted doses are not made up.(Romidepsin doses may be given up to 3 days late)

• If no further dose reduction levels patient will be removed from study.

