## 10.2 Required Blood Parameters and Other Investigations Prior to Each Treatment

Before each dose of romidepsin, excluding cycle X, day 1 patients should be reassessed and the following criteria must be fulfilled:

- ANC is  $\geq 1.0$  K/ $\mu$ L.
- Platelet count is  $\geq 50$  K/ $\mu$ L.
- Serum potassium and magnesium are within normal range
  - In cycle 2 and beyond in Phase Ib and any cycle in Phase IIa, magnesium and potassium levels may be checked up to 3 days prior to administration of romidepsin. If levels are within range romidepsin may be administered without repeat testing unless clinically indicated (such as vomiting, diarrhea, or initiation of medications that may affect electrolytes).
  - Supplements must be given to patients whose potassium and/or magnesium are below normal range.
    - Magnesium supplementation: If levels are below normal range, but  $\geq 1.2$  mg/dL, patients can receive at least 2gm magnesium IV and proceed to treatment without re-checking labs. Patients can be treated if magnesium levels are above normal range.
    - Potassium supplementation: If levels are below normal range, but  $\geq 3.2$  mEq/L, patients can receive at least 20mEq potassium IV and proceed to treatment without re-checking labs.
- Any clinically significant non-hematological toxicity to  $\leq$  Grade 2 .
- ECG schedule as specified in Table 7.
- If any of these criteria are not fulfilled, then administration of study drugs should be delayed as detailed in Section 9.0.

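### After grade 3 rash or neuropathy, Section 9.7.1 reduces both drugs one level but the Table 5 rows reduce lenalidomide only, so the level at which romidepsin resumes is undetermined

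*Combined protocol and SAP*

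**What the plan says.** Section 9.7.1 introduces its bullets and the tables as one set of rules: "Dose delay and dose reduction rules for lenalidomide and romidepsin are as follows and summarized in the tables 3, 4, & 5". One bullet covers a dose reduction due to "non-hematologic toxicity attributed to study drugs, lenalidomide and romidepsin will be reduced one level per Tables 3 & 4". It makes no exception for rash, neuropathy or thyroid dysfunction.

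Table 5 treats these toxicities differently. For grade 3 non-blistering rash and for grade 3 neuropathy it says "If Grade 3, hold lenalidomide dose. Follow at least weekly". The rash row continues "If the toxicity resolves to grade 1, resume lenalidomide at next lower dose level", and the neuropathy row has the same content. Romidepsin appears in neither. The row for hyper- or hypothyroidism, which states no grade, omits lenalidomide for the rest of the cycle and then says "See Instructions for Initiation of a new cycle and reduce the dose of lenalidomide by 1 dose level". By contrast, the row for other non-hematologic toxicity of grade 3 or higher says "Hold lenalidomide and romidepsin dose. Follow at least weekly" and resumes both drugs one level lower. The neutropenia, thrombocytopenia and venous thrombosis rows also name both drugs.

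Section 10.2 sets conditions before each romidepsin dose other than day 1. One is "Any clinically significant non-hematological toxicity to" grade 2 or lower. It adds: "If any of these criteria are not fulfilled, then administration of study drugs should be delayed as detailed in Section 9.0". Section 9.7 says in general terms that a dose is held when treatment criteria are not met. Section 10.1 does not let a new cycle start until drug-related maculo-papular rash or neuropathy is grade 1 or lower.

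**The concern.** The 9.7.1 bullet and the Table 5 rows cannot both be followed on one question: the romidepsin dose level after a grade 3 rash or neuropathy has led to a lenalidomide reduction. Under the bullet, romidepsin also goes down one level. Under the rows, only lenalidomide changes. No text says which prevails.

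The event is central to this trial. Under Section 4.1, an attributed non-hematologic toxicity of grade 3 or higher is a DLT in cycle 1 of phase Ib and in cycles 1 to 4 of phase IIa, and characterizing toxicity is part of the primary objective. The toxicities are plausible here. Section 3.2.3.2 reports dose-limiting skin toxicity at lenalidomide 25 mg in cutaneous T-cell lymphoma, which this trial enrolls. Section 11.1 lists neuropathy as a side effect of romidepsin, so one cannot assume that romidepsin is irrelevant to that row. In a multicenter study, sites that read different places could deliver different romidepsin exposure after the same event. Differences between sites in later toxicity and dose intensity would then partly reflect the reading of the protocol.

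**Working it through.** The plan gives no figure to reproduce. The check sets the instructions side by side and then adds up doses from the protocol's own tables.

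**Instructions for romidepsin**

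| Place | Held? | Reduced on resumption? | Recovery grade required |
|---|---|---|---|
| 9.7.1, non-hematologic bullet | not stated | yes, one level | not stated |
| Table 5, grade 3 rash and grade 3 neuropathy | not stated (lenalidomide held) | not stated (lenalidomide reduced) | grade 1, for lenalidomide |
| Table 5, thyroid | not stated (lenalidomide omitted) | not stated (lenalidomide reduced) | refers to new-cycle instructions |
| Table 5, other non-hematologic, grade 3 or higher | yes | yes, one level | grade 2 or lower |
| 9.7 with 10.2 (days 8 and 15) | yes, while criteria are unmet | not stated | grade 2 or lower |
| 10.1 (day 1) | new cycle not started | not stated | grade 1 or lower for drug-related maculo-papular rash or neuropathy |

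**Step 1: is the 9.7.1 bullet triggered?** It is conditional on a dose reduction for attributed non-hematologic toxicity. The rash and neuropathy rows require a lenalidomide reduction on resumption, so if the event is attributed the condition is met and the bullet calls for romidepsin to be reduced too. The rows do not. The same holds for the thyroid row if the event is attributed.

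**Step 2: is romidepsin held?** If the toxicity is clinically significant and above grade 2 on day 8 or 15, 10.2 blocks the dose and 9.7 supplies the hold. The Table 5 rows do not show it, so a site using the table alone would not see it.

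**Step 3: recovery thresholds.** The rash and neuropathy rows and 10.1 use grade 1; 10.2 uses grade 2. These may be meant for different drugs and different days, but the text does not say so.

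**Step 4: size.** Inputs: the phase IIa lymphoma dose of romidepsin, 14 mg/m2 on days 1, 8 and 15 (Section 9.3); the one-level step from 14 to 10 mg/m2 (Table 4); missed doses not made up (9.7.1). Assumed course: attributed, clinically significant grade 3 rash found on day 8, with recovery too late for the day 8 dose but in time for day 15.

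- Day 8 held, romidepsin not reduced: 14 + 0 + 14 = 28 mg/m2.
- Day 8 held, romidepsin reduced one level: 14 + 0 + 10 = 24 mg/m2.
- Each later dose: 14 versus 10 mg/m2, and (14 − 10)/14 = 28.6%.
- Each later full cycle: 3 × 14 = 42 versus 3 × 10 = 30 mg/m2, again 28.6% lower.

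The event-cycle comparison uses one clinical course and changes only the resumption rule.

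**The case against.** The strongest defense is that the specific governs the general: the bullet sets the size of a step through Tables 3 and 4, and Table 5 says which drug is stepped down for which toxicity. That reading is possible, but the text does not establish it. Section 9.7.1 presents Table 5 as a summary of its rules, not as a list of exceptions. Section 9.7.3 sends toxicities to Table 5 apart from those already mentioned, which does not rank the table above the bullet. Section 17.4 provides routine calls with sites about safety issues including DLTs. Calls may limit divergence but do not settle the wording.

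Other parts of the defense stand, and they rule out three stronger readings.

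- **Three incompatible actions for romidepsin (continue, delay, reduce).** A reader might infer this. But delay and reduction can run in sequence, exactly as in the row for other non-hematologic toxicity. The open question is the level on resumption.
- **One place allows romidepsin during an unresolved grade 3 toxicity that another forbids.** The Table 5 rows are silent on romidepsin; they do not say to continue it. Silence does not override the express condition in 10.2, and the reference from 10.2 to Section 9 does reach a hold instruction in 9.7.
- **A threefold range in one cycle, 14 to 42 mg/m2.** The 42 (3 × 14) requires ignoring 9.7 and 10.2. The 14 (14 + 0 + 0) requires toxicity above grade 2 through day 15. Setting these beside a case that recovers by day 15 mixes clinical courses with rules.

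It is also correct that the decision rules in Section 14.0 count patients with a DLT. A patient with such an attributed event inside the window is already counted, whatever happens to romidepsin afterwards.

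**Conclusion.** The contradiction is real and limited. Section 9.7.1 and the Table 5 rash, neuropathy and thyroid rows disagree on whether romidepsin is reduced, and those rows do not reflect the hold that 9.7 and 10.2 impose. For a patient who started at 14 mg/m2, sites could resume romidepsin 28.6% apart per dose, or 4 mg/m2 apart in the event cycle (28 − 24).

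This rests on four assumptions: the toxicity is attributed to study drugs, it is clinically significant in the sense of 10.2, the day 8 dose is missed, and recovery comes by day 15. The thyroid row has no grade, so the clear conflict there is with 9.7.1 only, and the event-cycle figure does not apply to it.

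The documents support saying that sites could dose differently, not that they would. Dose escalation and the phase IIa dose-reduction rule are not altered through the count of the initial event. What could vary by site is romidepsin exposure after it, recurrence of toxicity and dose intensity.

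**What to change.** Reconcile Sections 9.7.1, 10.1 and 10.2 with Table 5. Each non-hematologic row of Table 5 should state one action for each drug: held or not, level on resumption, and recovery grade required. Sections 9.7.1 and 10.2 should then refer to that row. If the sponsor intends lenalidomide-only reductions for some toxicities, the 9.7.1 bullet should be limited accordingly. If it intends both drugs to be reduced, the rows should say so. In either case, the text should show how the hold in 9.7 and 10.2 applies to these rows and which drug and day each recovery grade governs. The choice of clinical rule is the sponsor's.

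The cost is a wording amendment, with site ethics approval as for any amendment under Section 16.3, and retraining of sites. No patients or procedures are added.
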